Subjects will discontinue study treatment at the time of disease progression, development of unacceptable toxicity, withdrawal of consent, or qualifies any of the criteria described in '9.3.3.1 Discontinuation for Individual Subjects'. The discontinuation assessments will occur within 7 days and off-treatment visit on 30th day after the final dose of study treatment.

DLT is defined as toxicity related to this combination therapy as indicated below.

Table 1. Dose Limiting Toxicities (DLT)

Toxicity Category	Toxicity/CTCAE Grade
Hematologic	
 
• Grade 4 neutropenia lasting >7 days
 
• Grade 3 febrile neutropenia (axillary temperature <math>\geq 38.5^{\circ}\text{C}</math> and neutrophils <math>< 1 \times 10^3/\mu\text{L}</math> (<math>< 1000/\text{mm}^3</math>))
 
• Grade <math>\geq 3</math> thrombocytopenia lasting >7 days or requiring blood transfusion
 

Non-hematologic toxicity	
 
• Grade 3 non-hematologic toxicities lasting >7 days except for the following: 
 
➢ Clinically insignificant or transient abnormal laboratory findings
 
➢ Able to be controlled by maximal supportive therapy
 
 Grade <math>\geq 3</math> hyperamylasemia or hyperlipasemia without clinical or other evidence of pancreatitis are not regarded as a DLT. 
 
• Grade <math>\geq 3</math> Nausea, vomiting or diarrhea lasting >7 days despite maximal medical therapy
 
• Hypertension uncontrolled by medication
 
• Any thromboembolic event including cerebrovascular hemorrhage/events
 

Medication compliance	
 
• Failure to administer <math>\geq 75\%</math> of the planned dosage of lenvatinib or everolimus as a result of treatment related toxicity
 

Overall study design is presented below.

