- Severe (Grade 3) condition: Interrupt study treatment (lenvatinib and everolimus) and consider using adrenal cortical hormone. If it is resolved to Grade 0-1 or baseline, resume study treatment with lenvatinib alone after resolving to Grade 0-1 or baseline according to his/her clinical condition. Investigator will make a decision on whether the subject can resume the study treatment and if so, as well as the dose level. Everolimus must not be concomitantly administered.
- If a subject experiences life-threatening (Grade 4) event, both lenvatinib and everolimus must be discontinued.

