#### 9.4.11 Points to Consider on Determination of DLT

1. Grade 4 neutropenia is observed
  - a. Additional tests will be performed as needed to confirm duration of the event.
  - b. If Grade 4 is present on Day 8 and beyond (Day 1 defined as the day the event was confirmed to be Grade 4), the event will be judged as 'duration  $\geq 7$  days'. If the event doesn't resolve and hematology tests cannot be performed on Day 8, the investigator will discuss with sponsor on handling of the event. Consult with independent medical advisor, as needed.
2. Grade 3 or Grade 4 thrombopenia is observed:
  - a. Additional tests will be performed as needed to confirm duration of the event.
  - b. If Grade 3 or 4 continues on Day 8 and beyond (Day 1 defined as the day the event was confirmed to be Grade 3 or 4), the event will be judged as 'duration  $\geq 7$  days'. If the event doesn't resolve and hematology tests cannot be performed on Day 8, the investigator will discuss with sponsor on handling of the event. Consult with independent medical advisor, as needed.
3. Grade 3 or Grade 4 nonhematologic toxicities is observed
  - a. Additional tests will be performed as needed to confirm duration of the event.
  - b. If Grade 3 or 4 continues on Day 8 and beyond (Day 1 defined as the day the event was confirmed to be Grade 3), the event will be judged as 'duration  $\geq 7$  days. If the event doesn't resolve and hematology tests cannot be performed on Day 8, the investigator will discuss with sponsor on handling of the event. Consult with independent medical advisor, as needed.
4. If a subject experiences unexpected AEs that is not listed on 'Table 1 Dose Limiting Toxicity (DLT)' and requires discontinuation from treatment, investigator will discuss with sponsor on handling of the event. Consult with independent medical advisor, as needed.

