#### **Assessing Severity of Adverse Events**

AEs will be graded on a 5-point scale according to CTCAE v4.03. Investigators will report CTCAE grades for all AEs (for a change in severity).

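### The febrile neutropenia DLT row is labelled exactly Grade 3, so, read literally, a short or late Grade 4 episode in Cycle 1 can go uncounted

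*Protocol*

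**What the plan says.** DLT is the first-named primary endpoint (protocol Section 9.7.1.1, SAP Section 5.1.1). The hematologic part of the DLT table has three rows, worded alike in the synopsis, protocol Table 1 and SAP Table 1:

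- "Grade 4 neutropenia lasting" more than 7 days.
- "Grade 3 febrile neutropenia (axillary temperature" of at least 38.5°C, with neutrophils below 1 × 10³/µL).
- Thrombocytopenia of Grade 3 or higher, lasting more than 7 days or needing transfusion.

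The nausea, vomiting and diarrhea row is also open-ended at Grade 3 and above. The general non-hematologic row, like febrile neutropenia, carries a bare Grade 3.

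On grading, the protocol states that "AEs will be graded on a 5-point scale according to CTCAE v4.03". It uses Grade 4 to mean life-threatening, for example in Section 9.4.7: "If a subject experiences life-threatening (Grade 4) event, both lenvatinib and everolimus must be discontinued".

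Section 9.4.11 explains how to decide whether an event is a DLT. It has items for Grade 4 neutropenia, for Grade 3 or 4 thrombopenia, and for the case where "Grade 3 or Grade 4 nonhematologic toxicities is observed". It has none for febrile neutropenia. Its last item begins "If a subject experiences unexpected AEs that is not listed on" Table 1. It applies where the event requires discontinuation, and it leads to a discussion with the sponsor.

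**The concern.** A DLT count should not include an event and leave out a worse form of the same event. Followed to the letter, this row can do so: a Grade 3 febrile neutropenia counts, while a Grade 4 one with the same temperature and neutrophil count fails on the label alone. Because the same table marks other rows as Grade 3 or higher, a site could reasonably take the missing sign as intended. Another site could treat the bracketed limits as the whole definition. The same event could then be classified differently at different sites.

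The DLT count feeds two rules in protocol Section 9.1. Enrollment is interrupted at two or more subjects with a DLT, and a lower-dose cohort may be opened if more than one-third have one. DLT status also decides Cycle 1 dosing under Section 9.4.1.

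**Working it through.** The plan states no power, error rate or event rate that depends on this row, so there is no figure to reproduce. The check has three parts.

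**1. Which rows could still catch a Grade 4 febrile neutropenia in Cycle 1?**

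- *Neutropenia row.* It needs Grade 4 neutropenia for more than 7 days; Section 9.4.11 item 1 looks for Grade 4 on Day 8 of the event. SAP Section 13.1 puts Grade 4 neutrophils below 0.5 × 10⁹/L, whereas the febrile neutropenia limit is below 1 × 10⁹/L (the same as 1 × 10³/µL). A count between 0.5 and 1.0 with fever therefore meets the febrile neutropenia limits without any Grade 4 neutropenia.
- *Compliance row.* It counts failure to give at least 75% "of the planned dosage of lenvatinib or everolimus as a result of treatment related toxicity". The row names no denominator; I take 28 daily doses of each drug (one cycle). Seven missed: 21/28 = 75.0%, not a DLT. Eight missed: 20/28 = 71.4%, a DLT. For a permanent stop with the first withheld dose on Day d, the fraction given is (d − 1)/28. At d = 21 it is 71.4% and is caught; at d = 22 it is 75.0% and is not.
- *General non-hematologic row.* It is not the category in which the table places this event. It also needs more than 7 days and exempts toxicity controlled by maximal supportive therapy.
- *Section 9.4.11 item 4.* It gives a discussion at most.

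What remains uncaught is a Grade 4 febrile neutropenia with Grade 4 neutropenia for 7 days or less and fewer than 8 of 28 doses missed, for example with onset from Day 22.

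**2. What does one uncounted event do to the rules?**

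One subject is 1/6 = 16.7 points at n = 6 and 1/12 = 8.3 points at n = 12.

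| Subjects | Most DLTs not over one-third | Fewest DLTs over one-third |
|---|---|---|
| 6 | 2 (33.3%) | 3 (50.0%) |
| 9 | 3 (33.3%) | 4 (44.4%) |
| 12 | 4 (33.3%) | 5 (41.7%) |

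At n = 6, one event moves 1/6 to 2/6 (enrollment interrupted) or 2/6 to 3/6 (over one-third).

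**3. How much could this matter on average?**

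The documents give no rate for this event, so the rates here are assumptions. Let p be the DLT rate under the literal reading and q the rate of uncounted Grade 4 febrile neutropenia in subjects with no other DLT. With X ~ Binomial(6, p + q):

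| p | q | P(X ≥ 2) | P(X ≥ 3) |
|---|---|---|---|
| 10% | 0 | 0.114 | 0.016 |
| 10% | 1% | 0.134 | 0.021 |
| 10% | 5% | 0.224 | 0.047 |
| 20% | 0 | 0.345 | 0.099 |
| 20% | 1% | 0.369 | 0.112 |
| 20% | 5% | 0.466 | 0.169 |
| 30% | 0 | 0.580 | 0.256 |
| 30% | 1% | 0.601 | 0.274 |
| 30% | 5% | 0.681 | 0.353 |

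The 5% line is probably generous. Section 7.3.2.2 lists the Grade 3 or higher events seen in at least 5% of the Study 205 combination arm, and neither neutropenia nor febrile neutropenia is listed. With 51 subjects assigned, 2/51 = 3.9% and 3/51 = 5.9%, so at most two subjects had either event at Grade 3 or higher at any time.

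**The case against.** The strongest reply is that nobody meant to exclude Grade 4. Section 9.4.11 item 3 applies the duration rule to Grade 3 or 4 non-hematologic toxicity, although that row of Table 1 also says only Grade 3. The protocol therefore reads a bare Grade 3 as a floor at least once. A Grade 4 case also meets the bracketed limits. This stands as evidence of likely intent, and it makes the point a wording defect rather than a deliberate exclusion. It does not close the gap, because 9.4.11 gives febrile neutropenia no such extension and the neighbouring rows use the sign when they mean higher grades.

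Three stronger readings are tempting, and the documents do not support them:

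- *No Grade 4 febrile neutropenia could ever be a DLT.* Prolonged Grade 4 neutropenia counts through its own row, and cases losing 8 or more of 28 doses count through the compliance row.
- *Section 9.4.11 item 4 is closed because the event is expected.* Section 7.4 lists bone-marrow suppression and neutropenia but not febrile neutropenia, and the protocol does not define unexpected. Item 4 may be open, but it does not by itself make the event a DLT.
- *The lower-cohort decision turns on this row.* Section 9.1 also allows that cohort for unmanageable toxicity up to Cycle 2 or where tolerability cannot be confirmed. The rule is permissive, and the review weighs overall toxicity. At 2/6, enrollment has already been interrupted for review.

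It can also be said that the documents do not reproduce the CTCAE entry for febrile neutropenia; SAP Section 13.1 grades laboratory parameters only. That a Grade 4 exists for this term is inferred from the 5-point scale and the protocol's use of Grade 4 elsewhere.

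**Conclusion.** The defect is real but narrow. In all three tables the grade label is tighter than the limits printed beside it, and on a literal reading a short or late Grade 4 febrile neutropenia in Cycle 1 meets no DLT row. The discretionary tolerability review can take such an event into account, but it does not add a subject to the DLT count.

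The size is at most one subject per event: 16.7 points at n = 6 and 8.3 at n = 12, enough to cross either rule in a cohort of six. On average the effect is small if the event is rare. With an assumed 20% DLT rate and 1 point uncounted, P(at least 2 of 6) moves from 0.345 to 0.369. The conclusion rests on three assumptions: the label is applied literally, compliance is judged against 28 daily doses, and Grade 4 applies to febrile neutropenia as it does to other events in the protocol.

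**What to change.** Reconcile the row's grade label with its own fever and neutrophil limits and with Section 9.4.11, so that the DLT count does not omit an event more severe than one it includes. Put the same definition in the synopsis table, protocol Table 1 and SAP Table 1, and add a febrile neutropenia item to Section 9.4.11. If Grade 4 was left out on purpose, say so and give the reason.

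DLT status drives dosing, so two further places must be read together. Under Section 9.4.1, a Cycle 1 event that is not a DLT allows interruption at the investigator's judgment and resumption at the same dose level. The Grade 4 line of Table 2, written for Cycle 2 onward, calls for discontinuation. The sponsor should reconcile these for an event that is Grade 4 but not a DLT; which rule is right is a clinical decision outside this review.

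The cost is a few words in three tables and one item in 9.4.11, with no change to sample size or analysis method. The small downside is that a broader reading could slightly raise the DLT count.

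### The general non-hematologic DLT line says Grade 3 rather than Grade 3 or higher, so read literally a persistent Grade 4 event can go uncounted

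*Protocol*

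**What the plan says.** Protocol section 9.1 defines DLT as related toxicity listed in Table 1. The general non-hematologic line there is "Grade 3 non-hematologic toxicities lasting" more than 7 days. It excepts insignificant or transient laboratory findings and events that are "Able to be controlled by maximal supportive therapy". The synopsis table and SAP Table 1 (section 3.2.1) give the same grade.

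Other text goes beyond Grade 3:

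- Protocol 9.4.11 item 3 opens with "Grade 3 or Grade 4 nonhematologic toxicities is observed" and applies the Day 8 duration test to both grades. Its Day 1 definition, however, names one grade: "confirmed to be Grade 3), the event will be judged as". The parallel thrombocytopenia rule in item 2b has "confirmed to be Grade 3 or 4), the event will be judged as".
- Table 1 says that Grade ≥3 "hyperamylasemia or hyperlipasemia without clinical or other evidence of pancreatitis are not regarded as a DLT".
- The nausea, vomiting and diarrhea line is also written for Grade ≥3.

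Other Table 1 lines catch some Grade 4 events: uncontrolled hypertension, any thromboembolic event, and failure to take at least 75% "of the planned dosage of lenvatinib or everolimus as a result of treatment related toxicity".

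**The concern.** A table that defines a primary endpoint should not count the milder grade and omit the worse one. Section 9.4.11 item 3 shows the intent, but it is headed as points to consider and only judges duration. It does not say that a Grade 4 event is a DLT. The SAP repeats the table and not section 9.4.11.

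The count has consequences. Section 9.1 makes the enrollment pause mandatory once two subjects have a DLT. One counted DLT plus one uncounted Grade 4 event leaves the count at 1, and the pause is not triggered. The condition for opening the lower-dose cohort, more than one-third of subjects with a DLT, uses the same count.

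**Working it through.** There is no power or sample-size figure to reproduce, because the sample size is stated not to be statistically based. The check has three steps.

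**1. Which events fall in the gap.** A related Grade 4 non-hematologic event meets no criterion, read literally, only if all of these hold:

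- it lasts more than 7 days;
- it is outside the two listed exceptions;
- it is not nausea, vomiting, diarrhea, uncontrolled hypertension or thromboembolism;
- it does not take dosing below 75%.

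Grade 4 events that are shorter or controllable are not DLTs under either wording.

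**2. How far the 75% dose criterion reaches.** Cycle 1 has 28 daily doses, and 75% of 28 is 21. Seven missed doses give 21/28 = 75.0%, which is not a DLT. Eight give 20/28 = 71.4%, which is. With onset on cycle day d, event Day 8 is cycle day d + 7.

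| Dosing pattern | Caught for onset on | Not caught for onset on |
|---|---|---|
| Held from d through d + 7 (8 doses) | Days 1–21 | Days 22–28 |
| Onset-day dose taken, then 8 held | Days 1–20 | Days 21–28 |
| Onset-day dose taken, then 7 held | never | all |
| Dosing continued | never | all |

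Continued dosing is allowed: for a Cycle 1 event that is not a DLT, section 9.4.1 leaves interruption to the investigator's judgement. For onset from Day 22, event Day 8 falls after Day 28, so counting also depends on following duration past Cycle 1.

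**3. Effect on the decision rules, n = 6.** Let p be the per-subject probability of a counted DLT and q that of an uncounted Grade 4 event. Let x and y be the numbers of subjects with each. Then

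P(x, y) = 6! / [x! y! (6 − x − y)!] × p^x × q^y × (1 − p − q)^(6 − x − y).

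- Pause missed: sum over x ≤ 1 and x + y ≥ 2.
- One-third condition missed: sum over x ≤ 2 and x + y ≥ 3, since 2/6 = 33.3% is not over one-third and 3/6 = 50.0% is.

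The value p = 1/11 comes from the 18 mg/5 mg cohort in protocol section 7.3.2.1 (1 DLT in 11 subjects). The values 1/5 and 1/3 are assumed. The documents give no value for q, so it is assumed too. None of the 4 DLTs among the 20 subjects in that section was Grade 4, but this does not estimate q.

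As an example, at p = 1/5 and q = 0.01 the leading term for a missed pause (x = 1, y = 1) is 30 × 0.2 × 0.01 × 0.79^4 = 0.0234, out of a total of 0.0246.

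| | q = 0.1% | q = 0.5% | q = 1% |
|---|---|---|---|
| Pause missed, p = 1/11 | 0.0019 | 0.0095 | 0.0192 |
| Pause missed, p = 1/5 | 0.0025 | 0.0123 | 0.0246 |
| Pause missed, p = 1/3 | 0.0020 | 0.0098 | 0.0195 |
| One-third missed, p = 1/11 | 0.0004 | 0.0020 | 0.0041 |
| One-third missed, p = 1/5 | 0.0012 | 0.0062 | 0.0127 |
| One-third missed, p = 1/3 | 0.0020 | 0.0099 | 0.0199 |
| At least one such event, 1 − (1 − q)^6 | 0.0060 | 0.0296 | 0.0585 |

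**The case against.** The strongest reply is that this is a drafting slip with an obvious intended reading. Section 9.4.11 was written for determining DLTs and names Grade 4, so an undercount requires investigators to set it aside. SAP Table 1 only restates the design, and the SAP gives no rule for re-deriving DLTs from grade. All of this is fair. It makes an undercount unlikely, but the text that defines DLT still says something else, and three to five sites should not have to infer the rule.

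Second, there are further safeguards:

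- Sections 9.4.4 and 9.4.7 stop both drugs for hepatic failure and for Grade 4 interstitial lung disease, with no cycle limit. A permanent stop by Day 21 misses at least 8 doses and is caught.
- Table 2 stops treatment for Grade 4, but section 9.4.1 applies it from Cycle 2.
- Section 9.4.11 item 4 covers unexpected events not listed in Table 1: "and requires discontinuation from treatment, investigator will discuss with sponsor on handling of the event". That leads to a discussion and not to a counted DLT.

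These make the gap rarer without closing it.

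Third, for onset on Days 22–28 a Grade 3 event has the same difficulty with follow-up past Day 28. That stands: the wording change alone does not settle those cases.

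Fourth, the one-third figures overstate the consequence. In about 90% to 99.7% of those cases exactly two DLTs were counted, so enrollment is already interrupted and under review. The condition is also permissive and sits beside a review of overall toxicity up to Cycle 2. This stands too, and it makes the mandatory pause the consequence that matters.

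**Conclusion.** The concern holds as a minor error in the definition of a primary endpoint. The three tables disagree with section 9.4.11 item 3 on which grades count, and the literal reading omits the more severe grade. The events affected are few: persistent, uncontrolled Grade 4 events outside the named categories, with no more than 7 Cycle 1 doses missed. With q assumed between 0.1% and 1%, and p between 1/11 and 1/3, the chance of missing the pause in six subjects is about 0.2% to 2.5%. An undercount is possible and has not been shown. The event would still appear in the adverse event tables.

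**What to change.** Write Grade ≥3 in the general non-hematologic line of the synopsis table, protocol Table 1 and SAP Table 1. In protocol 9.4.11 item 3b, define Day 1 as the day Grade 3 or 4 is confirmed, as item 2b already does.

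The cost is a few words in four places, with no added patients, visits or tests. The observed DLT rate may come out slightly higher and enrollment may pause slightly more often.

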**Figure 1 Study Design**

**9.1.1 Pretreatment Period**

Pretreatment Period will consist of obtaining informed consent, screening procedures, subject enrollment and baseline assessments. Each subject must be explained the nature of the study and sign an informed consent form before any study-specific procedures are performed. Investigators must confirm the eligibility of each subject during screening procedures.

All Screening procedures are to be completed within 28 days prior to the Cycle 1 Day 1 and eligible subjects will be enrolled. All Baseline assessments are to be completed within 7 days prior to the Cycle 1 Day 1 and subjects' eligibility will be confirmed.

**9.1.1.1 Treatment Period**

Treatment Period will consist of two parts: Cycle 1 and following cycles.

One treatment cycle is defined as 28 days. Lenvatinib will be administered at starting dose of 18 mg in combination with everolimus at starting dose of 5 mg both orally once daily continuously. DLT will be observed during Cycle 1 (28 days following the initial dosing) to investigate tolerability and safety. Treatment will continue until disease progression, development of unacceptable toxicity, subject requests to discontinue, withdrawal of consent, or study termination by sponsor.

Subjects will be required to stay at the clinic during Cycle 1 in principle, however, they may be allowed to go home temporarily, be discharged or receive treatment as outpatient per investigators' discretion.

### 9.1.1.2 Follow-up Period

Follow-up Period will include discontinuation assessments and off-treatment visit. Subject will discontinue study treatment if he/she qualifies for any of the criteria listed in Section 9.3.3.1. The discontinuation assessments will occur within 7 days and the off-treatment assessments on 30 days (+ 7 days) after the final dose of study treatment.

## 9.2 Discussion of Study Design, Including Choice of Control Groups

Control group is not employed in this study. Rationale of study design is described in Section 7.5 'Study Rationale' of this protocol.

## 9.3 Selection of Study Population

A total of 6 to 12 subjects will be enrolled in 3 to 5 investigational sites in Japan. Subjects who meet all of the inclusion criteria or none of the exclusion criteria will be eligible to receive study drug.

### 9.3.1 Inclusion Criteria

1. Subjects must meet all of the following criteria to be included in this study: Voluntary agreement to provide written informed consent of this study
2. Willing and able to comply with all aspects of the protocol after being fully informed of the content
3. Males or females aged  $\geq 20$  years at the time of informed consent
4. Histological or cytological confirmation of RCC
5. Subjects must have confirmed diagnosis of unresectable advanced and/or metastatic RCC
6. Disease progression following VEGF targeted therapy
7. Eastern Cooperative Oncology Group (ECOG) Performance Status (PS) of 0 to 1
8. Adequately controlled blood pressure with or without the use of antihypertensive agents (defined as BP  $\leq 150/90$  mmHg at screening and no change in antihypertensive therapy within 1 week prior to the Cycle 1 Day 1
9. Subjects with adequate function of major organs:
  - a. Hemoglobin  $\geq 9.0$  g/dL
  - b. Neutrophil count  $\geq 1.5 \times 10^3 /\mu\text{L}$
  - c. Platelets  $\geq 10 \times 10^4 /\mu\text{L}$
  - d. Total bilirubin  $\leq 1.5 \times$  upper limit of normal specified by the testing laboratory (ULN)
  - e. Alkaline phosphatase (ALP), AST and ALT  $\leq 3.0 \times$  ULN ( $\leq 5.0 \times$  ULN for patients with the liver metastasis)
  - f. Creatinine clearance  $\geq 40$  mL/min calculated per the Cockcroft and Gault formula  
Male:  $(140 - \text{age}) \times \text{weight (kg)} \div 72 \times \text{Serum creatinine (mg/dL)}$   
Female:  $0.85 \times (140 - \text{age}) \times \text{weight (kg)} \div 72 \times \text{Serum creatinine (mg/dL)}$

10. Adequate blood coagulation function, defined as international normalized ratio (INR)  $\leq 1.5$
11. Survival expectation of 3 months or longer after study enrollment
12. Washout period required from the end of prior treatment to the start of study drug administration will be as follows:
  - a. Anticancer therapies:
    - Other investigational drug or antibody therapy:  $\geq 4$  weeks
    - Chemotherapy (except small-molecule targeted therapy), surgical therapy, radiation therapy:  $\geq 3$  weeks
    - Endocrine therapy, immunotherapy, small-molecule targeted therapy:  $\geq 2$  weeks
  - b. Supportive therapies:

Blood transfusion, blood preparations, hematopoietic growth factors including G-CSF preparations:  $\geq 2$  weeks
13. Females of childbearing potential must not have had unprotected sexual intercourse within 28 days before subject registration and must agree to use a highly effective method of contraception (e.g., use of an intrauterine device, condom with spermicide\*, a contraceptive implant\*\*, an oral contraceptive\*, or have a vasectomized partner with confirmed azoospermia)Note throughout the entire study period and for 30 days after final administration of investigational drug. If currently abstinent, the subject must agree to use a double-barrier method as described above if she becomes sexually active during this study period or for 30 days after investigational drug discontinuation. Females who are using hormonal contraceptives must have been on a stable dose of the same hormonal contraceptive product for at least 4 weeks before administration and must continue to use the same contraceptive during this study and for 30 days after investigational drug discontinuation.

All females will be considered to be of childbearing potential unless they are postmenopausal (amenorrheic for at least 12 consecutive months, in the appropriate age group and without other known or suspected cause) or have been sterilized surgically (i.e., bilateral tubal ligation, total hysterectomy or bilateral oophorectomy, all with surgery at least one month before administration

Females of childbearing potential must not have had unprotected sexual intercourse within 28 days before subject registration and must agree to use a highly effective method of contraception (e.g., use of an intrauterine device, condom with spermicide\*, a contraceptive implant\*\*, an oral contraceptive\*, or have a vasectomized partner with confirmed azoospermia)Note throughout the entire study period and for 30 days after final administration of investigational drug. If currently abstinent, the subject must agree to use a double-barrier method as described above if she becomes sexually active during this study period or for 30 days after investigational drug discontinuation. Females who are using hormonal contraceptives must have been on a stable dose of the same hormonal contraceptive product for at least 4 weeks before administration and must continue to use the same contraceptive during this study and for 30 days after investigational drug discontinuation.

All females will be considered to be of childbearing potential unless they are

postmenopausal (amenorrheic for at least 12 consecutive months, in the appropriate age group and without other known or suspected cause) or have been sterilized surgically (i.e., bilateral tubal ligation, total hysterectomy or bilateral oophorectomy, all with surgery at least one month before administration).

Note: Whether or not a pharmaceutical agent or medical device has been approved and certified in Japan (\* : yes, \*\* : no)

14. Male subjects must have had a successful vasectomy (confirmed azoospermia) or they and their female partners must meet the criteria above (i.e., not of childbearing potential or practicing highly effective contraception throughout the study period and for 30 days after study drug discontinuation).

